9.9 Cohort and dose escalation stopping criteria

After each cohort a Safety Review Committee will review and assess all the available safety and PK study data from all of the cohorts to date in order to make a decision on the dose for the next cohort of subjects.

Data from a minimum of 14 subjects from the previous cohort must be reviewed before a decision to escalate can be taken.

The stopping criteria listed below apply to stopping during a cohort or at the end of a cohort during safety data review. Events that occur during the cohort will be passed onto the unblinded safety reviewers who will inform the study team of whether stopping criteria have been fulfilled and in such a case no other subjects will be enrolled. Subjects on treatment will be asked to stop dosing and if possible go through the early termination assessments.

1. One subject who has received NT-814 reports a serious adverse event which is considered at least possibly related to the NT-814
2. Two or more subjects, who have received NT-814, have QTc prolongation, defined as QTc > 500 ms for both Bazett and Fridericia corrections, or a prolongation from baseline of > 60 ms, confirmed (persistent for at least 5 min) during continuous ECG monitoring deemed to be at least possibly related to study drug (discovered at the end of the cohort during safety data review or on repeat ECGs taken during the study at the pre-determined time points or at the time of an AE)
3. Two or more subjects, who have received NT-814, have tachycardia, defined as resting supine heart rate > 125 beats per minute persisting for at least 10 minutes deemed to be unrelated to a hot flash episode and at least possibly related to study drug during continuous ECG monitoring (discovered at the end of the cohort during safety data review or on a repeat ECGs taken during the study at the pre-determined time points or at the time of an AE)
4. Two or more subjects, who have received NT-814, have symptomatic bradycardia, defined as resting supine heart rate < 45 beats per minute or asymptomatic bradycardia defined as resting supine heart rate < 30 beats per minute while awake persisting for at least 10 minutes during continuous ECG monitoring deemed to be at least possibly related to study drug (discovered at the end of the cohort during safety data review or on a repeat ECGs taken during the study at the pre-determined time points or at the time of an AE)

5. Two or more subjects, who have received NT-814, develop hypotension, defined as an asymptomatic fall in Systolic blood pressure (SBP) > 20 mmHg to below 70 mmHg persisting for at least 10 minutes, or a symptomatic fall in resting supine SBP > 20 mmHg (excluding vasovagal reaction or associated with hot flashes) deemed to be at least possibly related to study drug
6. One or more subjects, who have received NT-814, fulfill Hy's law, defined as "an increase in AST or ALT ≥ 3 x upper limit of normal (ULN) and total bilirubin (TBL) ≥ 2 x ULN, where no other reason can be found to explain the combination of increases, e.g., elevated serum alkaline phosphatase (ALP) indicating cholestasis, viral hepatitis, another drug. The elevations do not have to be at the same time or within a specified time frame"
7. Two or more subjects, who have received NT-814, have > 3 x ULN of either ALT or AST, or > 2 x ULN for bilirubin or ALP deemed to be at least possibly related to study drug
8. Two or more subjects, who have received NT-814, have clinical and biochemical signs suggesting dehydration as assessed by the Investigator and Sponsor (weight loss $> 10\%$ from baseline, loss of skin turgor and biochemical signs such as increased serum urea and creatinine, high urinary osmolality and sediment) deemed to be at least possibly related to study drug
9. Two or more subjects, who have received NT-814, have sustained oxygen saturations below 90% that does not increase after administration of supplemental oxygen, deemed to be at least possibly related to study drug.
10. Two or more subjects, who have received NT-814, with clinically relevant cardiovascular AEs such as ventricular tachycardia or atrial fibrillation deemed to be at least possibly related to study drug
11. Dose escalation will not occur if the exposure of NT-814 is predicted to exceed a geometric mean AUC of 20950 ng.h/mL

9.10 Premature termination of study

The study may be terminated prematurely if:

- The Investigator and the Sponsor assess that the number and/or severity of AEs justify discontinuation of the study
- The Sponsor considers the applied doses of the study drug to be no longer relevant
- The Sponsor decides to discontinue the study

- Data not known before become available and raise concern about the safety of NT-814 so that continuation would pose potential risks to the subjects

Premature termination of the study must be mutually agreed upon by the Investigator and the Sponsor and must be documented. However, study results will be reported according to the requirements outlined in this clinical study protocol as far as applicable.

9.11 Treatment accountability and compliance checks

In accordance with regulatory requirements, the Investigator or designated site staff must document the amount of study medication dispensed and/or administered to study subjects, the amount returned by study subjects, and the amount received from and returned to the Sponsor (or representative) when applicable. Product accountability records must be maintained throughout the course of the study.

The Investigator is responsible for investigational product accountability, reconciliation, and record maintenance. The Investigator or designated site staff (e.g., storage manager, where applicable) must maintain IMP accountability records throughout the course of the study. The responsible person(s) will document the amount of investigational product received and returned (on behalf of NeRRe) and the amount administered to subjects. The accountability unit for this study is a capsule. Discrepancies are to be reconciled or resolved. Procedures for final disposition of unused investigational product will be provided in the Pharmacy Manual.

The Investigator has overall responsibility in ensuring that the study treatment is received and managed at the study site in accordance with GCP.

Limited responsibility may be delegated to a nominated study site representative and this delegation must be documented. Study treatment will be dispensed by a nominated person at each study site.

The Sponsor will be permitted upon request to audit supplies, storage and dispensing records and procedures.

9.12 Treatment blinding code

Study investigators will be given access to the IWRS system for the purposes of emergency unblinding. Investigators are permitted to unblind treatment for a subject if it is deemed that the subject's treatment will impact subject's future medical care. If possible, the Sponsor should be notified prior to the blind being broken, if not possible, the Sponsor must be notified as soon as possible if a code break was performed.

If a serious unexpected adverse reaction occurs requiring expedited reporting to the relevant regulatory agency / Institutional Review Board (IRB), then the blind will be broken for the relevant subject by the CRO safety group, in order to provide the regulators the knowledge of the event and

the causal agent. This is in agreement with ICH E2A and a blinded copy of the report will be provided to the investigators and the relevant IRB.

If unblinding occurs accidentally, this must be documented in the subject's medical notes and in the trial master file (TMF), and the Sponsor must be informed.

As detailed in Section 10.7, in the case of any safety concern or any ambiguous data, an unblinded Safety Review Committee will be permitted to review unblinded data for either individual subjects or the entire cohort to enable decision making.

9.13 Study restrictions

9.13.1 Permitted concomitant medications

All concomitant medications taken during the study will be recorded in the electronic case report form (eCRF) with indication, dose information, and dates of administration.

9.13.2 Prohibited concomitant medication

Subjects using the following medications will be excluded from the study:

- Any antidepressants (e.g. SSRI, SNRIs) within 4 weeks of Screening Visit
- NK receptor antagonists within 2 weeks of Screening visit
- Women on tamoxifen (or other estrogen modulating drugs) or receiving chemotherapy/radiation therapy within 4 weeks of Screening or planned antineoplastic chemotherapy/radiation therapy
- Drugs or herbal medications that could be associated with hot flash like symptoms including nicotinic acid, calcium channel blockers, clonidine, opioid drugs, black cohosh within 2 weeks of Screening Visit
- Drugs that are highly protein bound e.g. Warfarin and digoxin within 4 weeks of screening visit, use of non-steroidal anti-inflammatory drugs from the time of signing informed consent
- Use of any of the following hormonal treatment before Screening Visit:
 - 1 week or longer for prior vaginal hormonal products (rings, creams, gels)
 - 4 weeks or longer for prior transdermal estrogen alone or estrogen/progestin products
 - 12 weeks or longer for prior oral estrogen and/or progestin therapy
 - 3 months or longer for prior progestin implants and estrogen alone injectable drug therapy
 - 6 months or longer for prior estrogen pellet therapy or progestin injectable drug therapy

- Subjects using the following medications within 2 weeks prior to first dosing (or within 5 times the half-life of that medication, whichever is longer) will be excluded from the study:
 - Inhibitors of CYP3A4 (including but not limited to macrolide antibiotics, HIV protease inhibitor, azole antifungal drugs, cyclosporine, calcium channel inhibitor, cimetidine),
 - Inducers of CYP3A4 (including but not limited to rifampicin, carbamazepine, efavirenz, bosentan, modafinil, St. John's Wort),
 - Known P-glycoprotein inhibitors (including but not limited to amiodarone, azithromycin, carvedilol, clarithromycin, conivaptan, cyclosporine, diltiazem, dronedarone, erythromycin, felodipine, itraconazole, ketoconazole, lopinavir and ritonavir, quinidine, ranolazine, verapamil).
- Known CYP3A4 substrates with narrow therapeutic range are not allowed from screening until up to 5 half-lives after last dose of NT-814 is administered (including but not limited to alfentanil, cyclosporine, dihydroergotamine, ergotamine, fentanyl, pimozide, quinidine, sirolimus, tacrolimus).

As the inhibition potential of NT-814 with Breast Cancer Resistance Protein (BCRP) transporter has not yet been evaluated in vitro, an interaction with statins cannot be ruled out. Subjects receiving statins can be allowed into the study, but should be monitored for signs and symptoms of rhabdomyolysis and will be withdrawn from the study if these are observed.

Subjects will be required to inform the study investigator of any regularly taken medications (prescription or over the counter (OTC)), including hormone replacement therapy, natural and herbal products, vitamin, mineral or dietary supplement, taken within 2 weeks (or less than 5 times the half-life of that medication, whichever is longer) prior to first dosing. Use of such medications should be reviewed with the medical monitor and permitted on a case by case basis.

9.13.3 Dietary restrictions

Subjects must refrain from eating grapefruit, grapefruit juice, Seville oranges and pomelos within 7 days prior to Day -1 until after their final follow-up visit. Other than this restriction subjects should maintain their usual diet during outpatient periods of the study.

Subjects will be required to fast from midnight prior to dosing on Days 1, 7 and 14, for up to 4 hours after. Subjects are required to continue fasting until 4 hours post dose on these days. Water will be allowed *ad libitum*. On all other dosing days, the capsules must be taken on an empty stomach and no food is to be consumed for 4 hours following administration.

9.13.4 Other restrictions

If subjects experience somnolence or drowsiness at any time after discharge on Day 8 until they return to the clinic on Day 14 they should not drive or operate heavy machinery.

10. STUDY SCHEDULE

Table 2: Schedule of Events

| Procedure | Visit 1 Screen | Visit 2 | | | | Visit 3 | | Outpatient visits | | Early term visit ¹² | Follow-up Phone call ¹¹ |
|---|-------------------|----------------|----------------|-------|-------|----------------|--------|-------------------|--------|--------------------------------------|---------------------------------------|
| | | Day -1 | Day 1 | Day 7 | Day 8 | Day 14 | Day 15 | Day 16 | Day 17 | | Day 21 |
| Informed Consent ¹ | X | | | | | | | | | | |
| Medical History/ Concomitant Diseases | X | X | | | | | | | | | |
| Physical Examination | X | | X | | X | | X | | | X | |
| Inclusion/Exclusion criteria | X | X | X ² | | | | | | | | |
| Outpatient visit | X | | | | | | | X | X | X | |
| Admission | | X | | | | X | | | | | |
| Inpatient stay | | ←————→ | | | | ←————→ | | | | | |
| Discharge | | | | | X | | X | | | | |
| Randomization | | | X | | | | | | | | |
| Vital signs ³ | X | X | X | X | X | X | X | | | X | |
| 12-lead ECG | X | X ⁴ | X ⁴ | X | X | X ⁴ | | | | | |
| Hot flash paper diary ⁵ | X | X | X | X | X | X | X | | | | |
| Day time continuous hot flash paper diary ⁵ | | X | X | X | | X | | | | | |
| Sternal Skin conductance monitor ⁶ | | X | X | X | | X | | | | | |
| Holter monitor ⁶ | | X | X | X | X | X | X | | | | |
| AE/SAE recording | X | X | X | X | X | X | X | X | X | X | X |
| Dose medication ⁷ | | | ←————→ | | | | | | | | |
| Medication Dispensed ⁷ | | | | | X | | | | | | |
| Biochemistry/ Hematology | X | X | | | X | X | | | | X | |
| Urinalysis | | X | | | X | X | | | | X | |
| LH ^{8, 10} | | X | X | X | | | | | | | |
| estradiol, testosterone, FSH, ACTH, cortisol, TSH, T3 and T4 | | X | | | | | X | | | | |
| PK ^{9, 10} | | | X | X | | X | | X | X | | |

Key:

- 1 Informed consent must be signed by the subject before the start of any study procedure
- 2 Baseline assessments to be conducted on Day 1, prior to dosing. Key inclusion/exclusion criteria must be re-assessed before conducting any other baseline assessments
- 3 Vital signs include sitting and standing BP, heart rate, oral body temperature, pulse oximetry, respiration rate and weight will be performed daily during inpatient stays. Vital sign assessments will be performed on Day -1 at a similar time to the same assessments that are planned pre-dose on Day 1. The assessments will then be performed just prior to dosing (approx. 30 mins) for all other days in clinic and at a similar time on Day 15.
- 4 On Days 1 and 14, 12-lead ECG pre-dose and at 0.5, 1, 1.5, 2.0, 2.5, 3.0, 4.0, 8.0, 12.0 and 24.0 hours (all +/- 15 mins). The same assessments schedule is required on Day -1, starting at a similar time to that planned for Days 1 and 14. Once daily ECG recordings will be made just prior to dosing (approx. 30 mins) on all other days (Days 3-8) during inpatient stays.
- 5 Subjects need to complete paper-diary for the 2 weeks prior to Baseline visit to ascertain eligibility. Subjects also to record number of times awoken during the night due to flashes (Night time awakening (NTA). On Days -1 to 7 and on Day 14 subjects to record the occurrence and severity of the flash (scale 1 to 3) in a continuous diary. Diary to be provided to subjects during screening and at discharge on Day 8 and subjects instructed to start completing it after waking on the mornings of Day -1 and 14 prior to admission and throughout the day and night. In the inpatient treatment part of the study, subjects also push a button on the skin conductance monitor when they sense a hot flash
- 6 Skin conductance and Holter monitors to be fitted on Day -1 (24 hours prior to the planned study drug administration on Day 1) and remain in place until after the 24 hour assessments are completed on Day 8 and then for 24-hours from pre-dose on Day 14 to discharge on Day 15.
- 7 Study drug will be administered in the morning from Day 1 to Day 14. Study medication will be dispensed to the subject on Day 8 for self-administration at home (for Days 9 to 13).
- 8 LH sampling every 60 mins from time 0 (pre-dose on Day 1 and Day 7) to 8 hrs. The same sampling schedule is required on Day -1, starting at a similar time to that planned for Days 1 and 7.
- 9 PK Sampling at Pre-dose; 0.5; 1.0; 1.5; 2.0; 2.5; 3.0; 4.0; 5.0; 6.0; 8.0; 12.0; 24.0 hours; 48.0, 72.0 hours after Day 14 only.
- 10 Pre-dose samples for PK and LH to be taken within 30 minutes prior to dose administration
- 11 Telephone follow up visit, unless deemed by the investigator that a clinic visit is more appropriate to follow up an adverse event
- 12 Where possible, all subjects who are withdrawn or withdraw from the study early will undergo the Early Termination Visit assessments.
- 13 If the screening period is >28 days the following procedures must be repeated such that the most recent evaluation occurs within 28 days of the rescheduled randomization: biochemistry/hematology, vital signs, 12-lead ECG, physical examination. If the subject has completed (or partially completed) the screening twice daily Hot Flash Diary this must still be repeated and a new diary started on the new planned Day -15 and completed for the 2 weeks up to Day -2. Eligibility will be assessed on the repeated diary, not the initial one. If the subject had not started completing their screening diary at the time screening was put on hold, they will start this screening diary on the re-scheduled Day -15.

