As outlined in the IB, the non-clinical data for sex differences in PK measures are not clear and are contradictory. Allowing for a step wise dose escalation with adequate monitoring and PK based stopping limits is considered an appropriate means of conducting the study to allow for a comparison of PK across sexes and providing for the maximum chance of achieving full target engagement.

The C_{max} pharmacokinetic safety margin is based on the no-observed-adverse-effect-level (NOAEL) in the rat 3-month toxicity study. In this study GSK1144814A (vehicle, 5, 25 or 100 mg/kg/day) was given orally to rats for 13 weeks. There were no adverse, test-article related changes; therefore, the NOAEL was considered to be 100 mg/kg/day and corresponded to a geometric mean AUC of 95900 ng.h/mL and a geometric mean C_{max} of 6500 ng/mL. The use of rat data to determine C_{max} stopping criteria is felt to be acceptable as dose limiting toxicology in the most sensitive species (monkey) was related to total exposure (AUC) and not related to C_{max}, and there have been no adverse events (AEs) of concern related to C_{max} in the four Phase 1 clinical studies conducted thus far.

The study starting dose of 50 mg is anticipated to provide safety margins of approximately 12- and 14-fold respectively for AUC₀₋₂₄ and C_{max}. Subjects will be dosed and monitored in a controlled Phase 1 Unit clinic setting for the first 8 days of dosing and will only be escalated to the next cohort only when safety and PK data have been analyzed.

The target exposure of 14040 ng.h/mL (geometric mean AUC_{0-24} achieved with 200 mg daily dose in males for 28 days) gives a safety margin of approximately 3-fold against the 41900 ng.h/mL observed value while the predicted geometric mean C_{max} of 1836 ng/mL (at the 200 mg daily dose and after 14 days' administration) gives a safety margin of ~3.5 fold against the C_{max} .

No dose will be given that is expected to exceed a geometric mean AUC_{0-24} of 20950 ng.h/mL (2-fold safety margin).

As detailed in Section 10.7, the Safety Review Committee will evaluate safety and tolerability data from each cohort prior to escalating to the subsequent dose.

If study stopping criteria (see Section 9.9) have not been met and there are no concerning safety signals, the subsequent Cohort will proceed to the next dose.

If study stopping criteria are met, no further subjects will be dosed and the study will be terminated.

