4.10.3 Vital Signs

Vital signs will include sitting and standing BP, HR, arterial oxygen saturation, oral body temperature, respiration rate, and weight. Vital sign assessments will be performed on Day -1 at a similar time to the same assessments that are planned predose on Day 1. The assessments will then be performed postdose for all other days in clinic and at a similar time on Day 15.

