4.10.5 Electrocardiograms

On Days 1 and 14, resting 12-lead ECG data will be collected at the following timepoints: predose and at 0.5, 1.0, 1.5, 2.0, 2.5, 3.0, 4.0, 8.0, 12.0 and 24.0 hours (all +/- 15 mins).

The same assessment schedule is also required on Day -1, starting at a time similar to that planned for Days 1 and 14. The Day -1 and Day 1, 24 hour ECGs must be performed prior to the dose of study medication the following morning (on Days 1 and 2, respectively).

Once-daily ECG recordings will be just prior to dosing (approx. 30 mins) on all other days during the inpatient stay (Days 3 to 8).

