5 CHANGES IN THE CONDUCT OF THE STUDY OR PLANNED ANALYSIS

The conduct of the study and planned analyses are consistent with the study protocol (Version 4.0, dated 13 December 2016). The exposure response analysis on QTcB will not perform since this correction method is not regarded as appropriate ; per the Q&A E14, question 1.5 (available at http://www.ich.org/fileadmin/Public_Web_Site/ICH_Products/Guidelines/Efficacy/E14/E14_Q_As_R3_Step4.pdf).

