8 STATISTICAL METHODS

8.1 General

The statistical analysis will be conducted following the principles specified in the International Council for Harmonization, formerly the International Conference on Harmonization, Topic E9 Statistical Principles for Clinical Trials (CPMP/ICH/363/96).

All statistical tabulations and analyses will be done using SAS[®], Version 9.3 or higher.

Unless otherwise noted, continuous variables will be summarized using number of non-missing observations, arithmetic mean, standard deviation (SD), median, minimum, and maximum; categorical variables will be summarized using the frequency count and the percentage of subjects in each category.

In the data listings, study day relative to first dose of study drug may be presented. Study day relative to first dose will be calculated as: event date – first dose date (+ 1 if event date \geq first dose date). That is, there is no Day 0.

Baseline will be the latest available measurement prior to the first study drug administration in the study, unless otherwise specified.

For safety summaries, the unscheduled and repeat assessments will not be summarized; however, all results will be included in the data listing.

All subject level data, including those derived, will be presented in the individual subject data listings.

Unless otherwise noted, the analyses will be done by treatment (50 mg NT-814, 100 mg NT-814, 150 mg NT-814, etc... (XX mg NT-814), Total NT-814 (if applicable), placebo). Data for the placebo subjects will be combined across cohorts prior to any summaries.

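### All nine scheduled on-treatment blood pressure and oxygen saturation sets fall about 24 hours after a dose, and SAP 4.10.3 contradicts the protocol by calling them postdose

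*Protocol*

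**What the plan says.** **Protocol.** Table 2, note 3 has vital signs (sitting and standing blood pressure, heart rate, temperature, pulse oximetry, respiration rate, weight) taken daily during inpatient stays. The Day -1 set is matched in clock time to the pre-dose set on Day 1. After that: "The assessments will then be performed just prior to dosing (approx. 30 mins) for all other days in clinic", with Day 15 at a similar time. Section 10.4.9 refers back to Table 2.

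**SAP.** Section 4.10.3 repeats the sentence with a different time: "The assessments will then be performed postdose for all other days in clinic". Section 4.10.5 keeps the protocol's timing for the daily ECG: "Once-daily ECG recordings will be just prior to dosing (approx. 30 mins) on all other days during the inpatient stay". Section 5 states: "The conduct of the study and planned analyses are consistent with the study protocol". The only departure it names is dropping the QTcB exposure-response analysis.

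**Use of the data.** Change from baseline in vital signs, including oxygen saturation and postural blood pressure, is a safety endpoint (protocol 8.2). Vital signs are among the data reviewed before each escalation (10.7). In section 9.9, criterion 5 concerns hypotension and criterion 9 concerns sustained saturation below 90%. SAP 8.1 says of safety summaries that "the unscheduled and repeat assessments will not be summarized; however, all results will be included in the data listing".

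**The concern.** The trial gives ECG a dense postdose schedule and gives blood pressure and saturation none. ECG and Holter cover heart rate and rhythm; neither is described as measuring blood pressure or saturation. If NT-814 lowers either one for a few hours around peak and the effect wears off within the day, the scheduled readings would not show it.

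Two stopping rules depend on someone taking a measurement: the asymptomatic arm of criterion 5 (a fall of more than 20 mmHg to below 70 mmHg for at least 10 minutes) and criterion 9. Neither has a scheduled reading in the hours after a dose to prompt it.

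The SAP wording adds a reporting risk. A reader of the vital-sign table (Table 14.3.5.5) who relies on SAP 4.10.3 would take trough values as evidence about the postdose period.

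**Working it through.** The documents state no count of vital-sign sets, so there is no figure to reproduce. The count follows from the schedule.

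1. **Inputs.** Doses are given in clinic on Days 1 to 8 and Day 14, and at home on Days 9 to 13 (protocol 9.1). Vital signs are taken about 0.5 h before the dose on each clinic day, and at a similar time on Day 15 (note 3).

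2. **Sets after the first dose.** The Day 1 set is pre-dose, so it is baseline. Days 2 to 8 give 7, Day 14 gives 1 and Day 15 gives 1: 7 + 1 + 1 = 9.

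3. **Time since the previous dose.** 24 − 0.5 = 23.5 h for each set, or about 24 h if Day 15 runs slightly later. If the Day 13 home dose was missed, the Day 14 set is at 48 − 0.5 = 47.5 h. Sets within 12 h of a dose: 0 of 9. The early-termination set is contingent and untimed, and is not counted.

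4. **ECG for comparison (note 4).** There are 9 times from 0.5 to 12 h on each of Days 1 and 14: 9 × 2 = 18.

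5. **The SAP wording taken literally.** Eight of the sets (Days 2 to 8 and 14) would be postdose, at no stated time. Under the protocol none is.

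6. **How far trough may lie below peak.** Protocol 9.2 gives AUC0-24 of 14040 ng.h/mL and a predicted geometric mean Cmax of 1836 ng/mL at 200 mg. Average concentration = 14040/24 = 585 ng/mL, and 585/1836 = 0.319, about 32%. At steady state trough should not exceed the average, so 32% is an upper bound on trough over peak. It is indicative only, because the AUC is from men after 28 days and the Cmax is a prediction for Day 14. No Tmax is given.

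7. **The 50 mg margins are not a second bound.** The protocol says "The study starting dose of 50 mg is anticipated to provide safety margins of approximately 12- and 14-fold respectively for" AUC0-24 and Cmax. Dividing the 200 mg figures by four gives 14040/4 = 3510 and 1836/4 = 459. Then 41900/3510 = 11.9 and 6500/459 = 14.2, which are the stated margins. They appear to restate the same inputs.

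**The case against.** **Exposure is controlled.** No dose may be given that is expected to exceed a geometric mean AUC0-24 of 20950 ng.h/mL, half of the 41900 reached and tolerated in the repeat-dose study. The protocol adds that dose-limiting toxicity in the monkey followed AUC rather than Cmax, and that four Phase 1 studies showed no Cmax-related events of concern. This stands, and comparing milligram doses alone would overstate the risk. But those studies covered 89 men and 1 woman, and an AUC cap supplies no near-peak blood pressure or saturation data in women.

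**The stopping rules still work.** A reader might infer that criteria 5 and 9 cannot be triggered, or that postdose events would be hidden from the committee. The documents do not support that. Symptomatic falls can surface as adverse events, subjects are inpatients through Day 8 with frequent ECG and PK contact, and the committee is to "review and assess all the available safety and PK study data from all of the cohorts to date". Unscheduled readings are listed, though not summarized. What is missing is a planned reason to measure.

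**The SAP wording may be left over.** A reader might take the contrast with SAP 4.10.5 as showing a deliberate change, or as proof that readings were taken after dosing. The version history gives a simpler possibility. SAP 1.0 (01 December 2016) predates protocol 4.0 (13 December 2016), and version 2.0 lists only sections 4.1 and 4.10.5 as updated to follow it. First enrolment was planned for August 2016, and SAP 4.9 shows that PK sampling differed by cohort. Earlier cohorts may have had another vital-sign schedule, so the count of nine is established for version 4.0 only.

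**Posture.** Criterion 5's symptomatic arm refers to "a symptomatic fall in resting supine SBP > 20 mmHg", while only sitting and standing pressures are scheduled. A reader might call this a defect, but a supine reading suits an unscheduled bedside check of a symptomatic subject. No change is needed.

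**Conclusion.** The point holds in this form. Under protocol 4.0, nine of nine scheduled on-treatment blood pressure and saturation sets are at trough and none falls within 12 h of a dose, against 18 ECG times in that window. The vital-sign endpoint cannot describe blood pressure or saturation near peak. The asymptomatic arm of criterion 5 and criterion 9 have no scheduled postdose reading. SAP 4.10.3 contradicts the protocol, and SAP section 5 does not declare it.

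The count assumes that home doses were taken and that readings followed note 3. The 32% ratio assumes that the male AUC and the predicted Cmax can be set side by side.

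The documents do not show that any hypotension or desaturation was missed, or how large an effect this timing could miss. If an effect lasts the full 24 h, trough readings would show it and little is lost. The added readings are therefore a cheap improvement that should be made where still possible. The SAP wording is an error as it stands.

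**What to change.** 1. **For any cohort not yet dosed,** amend note 3 to add blood pressure and pulse oximetry at a few existing ECG and PK times, for example 2 and 4 h, adjusted to the Tmax seen in earlier cohorts. Do this on Days 1 and 14, and on Day 7 if practical, with the same clock times on Day -1 as baseline. Summarize by time after dose in Table 14.3.5.5.
2. **Check recorded vital-sign times by cohort,** then correct SAP 4.10.3 to match the protocol and the actual timing.
3. **Where only pre-dose readings exist,** label the vital-sign results as trough and draw no conclusion about blood pressure or saturation near peak.

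**Cost.** Two times on Days 1 and 14 plus two on Day -1 make 2 × 2 + 2 = 6 non-invasive sets per subject. Adding Day 7 makes 8, or 120 to 160 sets per cohort of 20. No extra visit or blood is needed. There is some crowding: the PK window is ±2 min at 2 h and ±5 min at 4 h, LH is ±5 min, and Day 7 has no serial ECG. Protocol 10.5 already ranks vital signs between ECG and PK. Section 10.7 lets the committee add times only where the data indicate it; otherwise an amendment is required.

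The planned last-subject date of 31 March 2017 and the May 2017 PK SAP, which lists four cohorts up to 300 mg, suggest that dosing may be over. In that case items 2 and 3 still apply and cost only a data check and wording.
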